11.3.2 Clinical Laboratory Evaluations

Descriptive statistics summarizing central laboratory data (hematology, chemistry, and coagulation) will be presented for all trial visits. Changes from pretreatment to each trial visit will also be summarized by treatment group/arm.

- a. The primary analyses of 90-day mortality will be carried out in an ITT framework using the logrank test or Cox regression. Time-to-death will be censored at 90 days or at liver transplant, whichever comes first. In addition to the logrank test, we will perform Cox regression analyses. The models will include baseline MELD score as well as other covariates deemed to be unbalanced or to effect survival. Tests will be performed at a two-sided nominal significance level of 5%. If the proportional hazard assumption is not met, we will compare the restricted mean survival time at 90 days.

Comparisons of binary survival indicators will be performed as alternative analyses, by using either chi-square tests or logistic regression models. In the logistic regression analysis, MELD score as well as other covariates deemed to be unbalanced or to effect survival will be included as covariates.

- b. We will also compare the transplant-free survival functions of the two treatment groups, at 30, 90 and 180 days.
- c. We will also secondarily compare the occurrence of events such as sepsis and renal dysfunction by using survival analysis (logrank test and Cox regression).

Before the groups are compared on these instruments, the baseline data will be examined to look for group imbalance among the survivors. Comparisons will be made using linear regression models that include baseline MELD score and other relevant and/or unbalanced covariates.

11.3.3 Additional Safety and Clinical Findings

Additional safety assessments include vital signs, lab results, and physical examinations. Descriptive statistics of the vital sign and lab measures will be provided; comparisons between the two treatment

groups will be made using mixed effects models. Changes of these variables from baseline at each visit will be analyzed similarly.

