2.3 Summary of Known Potential Risks with Study Medication

Corticosteroids (including prednisone) are the standard medical care for severe acute AH and have anti-inflammatory effects that can alter the body's reaction to other injuries. Prednisone may cause some, all or none of the side-effects listed below at the dose and duration used in the study.

Side effects	Frequent >20% of participants	Occasional 2 - 20% of participants	Rare Less than 2% of participants
Serious	Infection	Psychosis, Pancreatitis, Ulcerative esophagitis, Cushing's syndrome	Anaphylaxis, Hypersensitivity reaction, Peptic ulcer, Bone necrosis, Blood clot in a deep vein
Less Serious	Weight gain	High blood sugar, High blood pressure, Wound healing impairment, Increased intraocular pressure, Increased liver enzymes	Muscle weakness
Minor	Facial swelling Fluid retention Indigestion Increased appetite	Difficulty sleeping, Mood changes, Euphoria, Headache, Bruising	

Anakinra (study drug) is another anti-inflammatory treatment. It can alter the body's reaction to other injuries. Anakinra may cause some, all or none of the side-effects listed below at the dose and duration used in the study.

Side Effects	Frequent >20% of participants	Occasional 2 - 20% of participants	Rare Less than 2% of participants
Serious		Infection, including cellulitis, pneumonia and bone and joint infections)	Anaphylaxis, hypersensitivity reactions, Angioedema, Malignancy
Less Serious		Low blood count, (Neutropenia), Joint pain	Low blood count (Eosinophilia, Platelets), Nausea, Diarrhea
Minor	Injection site redness	Fever, Nasopharyngitis, Skin rash	

Zinc is an essential nutrient found in highest quantities in oysters, shellfish, meat, chicken, and fish. It is essential for the body's cells to function. When given in tablets, zinc may cause some, all or none of the side-effects listed below at the dose and duration used in the study.

Side effects	Frequent >20% of participants	Occasional 2 - 20% of participants	Rare Less than 2% of participants
Serious			
Less Serious	Nausea, Vomiting, Dizziness, Headache, Abdominal cramps, Diarrhea		
Minor	Indigestion		

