4. INVESTIGATIONAL PLAN

4.1 Overall Trial Design and Plan

Overview of Study Design and Conduct

The proposed study is a Phase 2b, multicenter, prospective, randomized, 2-arm, double blinded, placebo-controlled clinical trial to assess the efficacy of Anakinra, an IL-1 receptor antagonist plus zinc compared to prednisone for the treatment of severe AH (Model for End Stage Liver Disease (MELD) score ≥ 20). All participants will receive standard care for treatment of severe AH as described in recent guidelines endorsed by AASLD and AGA¹. The study will be conducted at **8 clinical sites** across the United States selected by the NIAAA and will be spearheaded by a **Data Coordinating Center (DCC-IU) at Indiana University**.

The study will be conducted according to good clinical practice (GCP) and in compliance with local, state, and federal regulatory requirements. Adverse events during the course of the trial will be identified, recorded, assessed for causality, and reported in accordance with FDA guidance. In addition to general assessment, we will specifically focus on (1) rates and types of infection as well as their severity, (2) potential development of drug-induced liver injury, (3) injection site reactions, and (4) hematological adverse events. These are related to the mechanisms of action of the drugs to be tested.

It is anticipated that this study will be approved by an appropriately convened single IRB and will be monitored by an NIAAA appointed data and safety monitoring board. We will conduct this study under an Investigational New Drug (IND) application from the United States Food and Drug Administration (FDA).

It is anticipated that a centrally located investigational pharmacy located at Indiana University will dispense the study medications to all participating sites under close coordination from the DCC- IU. Anakinra plus zinc and prednisone and matching placebos will be provided by the study to the participants.

Interventions to be tested

Concomitant treatments in this trial include standard care for severe AH for all participants as recommended in recent guidelines. The standard of care for severe AH includes attention to early diagnosis and treatment of bacterial and fungal infections, portal hypertension and its complications including acute kidney injury, gastrointestinal bleeding, fluid overload (ascites and edema) and hepatic encephalopathy. As part of the standard of care, all participants will be offered non-

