6.6.1 Treatment and holding/stopping rules for infection and sepsis

Leukocytosis is common in AH and may be further exacerbated by administration of prednisone. Such iatrogenic rise in leukocytosis may alarm participant care teams who are blinded to the treatment arm and may raise concern for development of infection or sepsis.

While many AH participants may develop the systemic inflammatory response syndrome (SIRS) (defined as two or more abnormalities in temperature, increased heart rate, respiration, or white blood cell count), SIRS may not always be indicative of infection in participants with AH and may be reflective of the dysregulated inflammatory state with AH.

Drug Holding Rules (Day 0-Day 30):

If one of the following criteria met, the study drugs should be held for 3 days:

1. Documented Infection
 - Pneumonia defined as new infiltrate by CXR or chest CT scan
 - Positive cultures (blood, ascites) for bacteria or fungus
 - Positive fungal cultures in urine ($> 50,000$ colonies/ml)
 - CNS infection defined as positive cultures or WBC > 5 in CSF
 - Severe soft tissue or bone infections including clinical diagnosis of cellulitis
2. SIRS (defined as two or more abnormalities in temperature, increased heartrate, respiration, or white blood cell count) with increase in SOFA score ≥ 2 points.

Participants will be reassessed on 3rd day to determine if study drugs could be resumed or should be stopped.

Drug Stopping rules (Day 0-Day 30):

Participants will be reassessed on third day of the study drugs hold: If infection clears and participant stabilizes, study drugs will be resumed.

1. For participants with documented infection: If infection is responsive to antibiotics and participant is stabilized or improved, study drugs may be resumed at the discretion of the clinical care team. If there is no improvement after 3 days, study drugs will be stopped.
2. For participants meeting only SOFA+SIRS criteria for stopping: if cultures of urine, blood, ascites, stool (including C. diff) are negative and CXR is unchanged, study drugs may be resumed at the discretion of the clinical care team.
3. If the participant has a second hold of study drugs due to infection/SOFA+SIRS criteria, study drugs will be stopped.
4. Participants in either arm who have a Lille score of >0.45 on day 7 will stop bottle 1 (prednisone/ placebo) and will continue with bottle 2 (zinc/zinc placebo.)

Drug stopping Rules (Day 0-Day 30):

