9.3 Clinical Laboratory

Blood samples for serum chemistry, hematology, and coagulation will be collected at every visit as detailed in the Schedule of Trial Procedures. The number and volume of samples to be collected at each visit will be detailed in a separate document. These tests will be conducted at local laboratories at 8 participating sites.

All participants with laboratory tests containing clinically significant abnormal values should be followed regularly until the values return to normal ranges, until a valid reason for the AE (other than study medication related AE) is identified, or until further follow up is deemed medically unnecessary.

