10.1.2 Severity of AEs

AEs must be graded for severity (i.e., intensity). A severity category of mild, moderate, or severe, as defined in Table 2, must be entered on the AE source document. It should be noted that the term “severe” used to grade intensity is not synonymous with the term “serious.” For example, severe headache is a severe AE, but may not be a serious AE. The assessment of severity is made regardless of study medication relationship or of the seriousness of the AE.

Table 2: Clinical Description of Adverse Event Severity

Grade	Clinical Description of Severity
1 = Mild	Causing no limitation of usual activities; the participant may experience slight discomfort.
2 = Moderate	Causing some limitation of usual activities; the participant may experience annoying discomfort.
3 = Severe	Causing inability to carry out usual activities; the participant may experience intolerable discomfort or pain.

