12.9 Publication Policy

No data are to be made public or published without prior knowledge and written approval by the AlcHepNet Consortium Steering Committee.

The AlcHepNet consortium publication policies will be applied.

LIST OF PLANNED LABORATORY ANALYTES

Serum Chemistry

sodium

potassium

calcium

chloride

bicarbonate

albumin

BUN

creatinine

total bilirubin

unconjugated (indirect) bilirubin

conjugated (direct) bilirubin

aspartate aminotransferase (AST; SGOT)

alanine transaminase (ALT; SGPT)

alkaline phosphatase (ALP)

glucose

total protein

MELD Score Calculation

<http://www.mayoclinic.org/meld/mayomodel6.html>

Lille Score Calculation

<https://www.mdcalc.com/lille-model-alcoholic-hepatitis>

Hematology

hemoglobin

hematocrit

WBC with differential

platelets

RBC count (incl. MCV, Hb [MCH], MCHC)

prothrombin time (PT and INR)

Urine and/or Serum pregnancy test

Special investigations

Pro-inflammatory cytokine/chemokines measurements (serum TNF- α , MCP1, IL-6, and IL-1 β)

Indicators of gut permeability (endotoxin and bacterial 18S DNA) and pro-inflammatory cytokine/chemokines (TNF α , MCP1, IL-6, IL-1 β)

EXPLORATORY EVALUATIONS

The following are the analyses that might be analyzed in the serum/plasma and peripheral blood mononuclear cells (PBMC): Cytokines/chemokines, NK cells, Cytotoxic T cells, Dendritic Cells (DC), Complement activation.

Table 5: Total Blood Volumes[¶]

Sample Type	Sample Blood Volume (ml)										Total Volume (ml)
	Screen	Day 0	Day 3	Day 7	Day 14	Day 28	Day 60	Day 90	Day 180		
Chemistry	5	5	5	5	5	5	5	5	5	40	
Hematology	3	3	3	3	3	3	3	3	3	24	
Coagulation	3	3	3	3	3	3	3	3	3	24	
Serum Pregnancy	3									3	
Biospecimen Banking [¶]		60		60	60	60	60	60	60	420	
Total	14	71	11	71	71	71	71	71	71	522	

[¶]These are estimated volume and may vary from center to center, depending on local laboratory requirements.

References

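### For neutropenia, a listed anakinra risk, the stated laboratory analysis compares values between arms and does not show how many participants had low counts or how low

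*Combined protocol and SAP*

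**What the plan says.** - **The risk.** The anakinra table in section 2.3 lists "Low blood count, (Neutropenia), Joint pain" in the less serious row, in the column for 2–20% of participants. Section 4.1 names four safety topics for specific attention; the last two are "3) injection site reactions, and (4) hematological adverse events".
- **The data.** The schedule in section 4.2 has a CBC at every visit, and the list of planned laboratory analytes includes "WBC with differential".
- **The laboratory analysis.** Section 11.3.2: "Descriptive statistics summarizing central laboratory data (hematology, chemistry, and coagulation) will be presented for all trial visits", with changes from pretreatment by arm. Section 11.3.3: "Descriptive statistics of the vital sign and lab measures will be provided; comparisons between the two treatment" groups are to use mixed effects models, and changes from baseline are handled in the same way.
- **The comparator.** Section 6.6.1: "Leukocytosis is common in AH and may be further exacerbated by administration of prednisone".
- **The adverse event route.** Section 10.1 allows an abnormal laboratory finding to be an adverse event. Section 11.3.1 tabulates treatment-emergent events by system organ class, preferred term, severity and relationship. Mild severity in Table 2 (section 10.1.2) reads "Causing no limitation of usual activities; the participant may experience slight discomfort"; the other two grades also rest on activity and discomfort.
- **The laboratories.** Section 9.3 says of the blood tests: "These tests will be conducted at local laboratories at 8 participating sites". Section 11.3.2 speaks of central laboratory data.

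**The concern.** Neutropenia is a lower-tail event in a minority of participants. The useful questions are how many fell below a given level, how far, and from what baseline. A mean or a mean change answers none of them. Here the mean is hard to read for a second reason: the comparator may push white cells up, so a lower average on anakinra is expected even if nobody becomes neutropenic.

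The adverse event tables are the other route, but they depend on each investigator deciding that a low value is clinically significant, and no neutrophil criterion guides that decision. When a case is recorded, its severity is graded by function, so a slight and a profound symptomless fall are both mild.

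What is at stake is the description of a named harm, relevant to infection in a population prone to it, from data that the trial already collects. The primary mortality result is not affected.

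**Working it through.** The plan gives no figure for this analysis beyond the 2–20% band. Its 85% power concerns mortality and has no bearing here.

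**1. Expected cases.** With 129 per arm (section 11.2), 129 × 0.02 = 2.6 and 129 × 0.20 = 25.8. Even at 2%, the chance of at least one case is 1 − 0.98^129 = 0.926.

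**2. How far neutropenia moves the mean.** Assumptions, none from the documents: neutrophil mean 8 and SD 5 (×10⁹/L), affected participants at 0.7, one cross-sectional comparison.
- SE of the difference = 5 × √(2/129) = 0.623.
- Shift = p × (8 − 0.7).
- Comparison for a threshold count: two-sided Fisher exact test at 5%, with an assumed 0.5% incidence on prednisone.

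| Incidence on anakinra | Shift in mean | Shift in SEs | Power, means | Power, threshold count |
|---|---|---|---|---|
| 2% | 0.146 | 0.23 | about 6% | about 3% |
| 5% | 0.365 | 0.59 | 9% | 45% |
| 10% | 0.730 | 1.17 | 22% | 95% |
| 20% | 1.460 | 2.35 | about 65% | above 99% |

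With mean/SD of 6/4 or 10/6, power for the means is 8–10% at 5% incidence and 19–24% at 10%. If incidence on prednisone is 2% instead of 0.5%, power for the count at 5% falls to about 15%.

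**3. How much of the mean contrast is neutropenia.** Suppose prednisone raises the mean by 20%: 0.20 × 8 = 1.6, or 1.6/0.623 = 2.57 SEs. With 5% neutropenia the total gap is 1.6 + 0.365 = 1.965, of which neutropenia supplies 0.365/1.965 = 19%. At 10% it supplies 0.73/2.33 = 31%. These shares do not depend on the SE, so a more precise mixed model would not change them.

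**4. A different model.** Take lognormal neutrophils with median 7 and log-SD 0.5 (mean 7 × e^0.125 = 7.93), affected participants at 0.8, and a 1.2-fold rise on prednisone. At 5% incidence the gap is 1.94, of which 0.36 is neutropenia: again 19%. With no prednisone effect, power for the means is about 10% at 5% incidence and 27% at 10%.

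**5. Severity.** Table 2 contains no laboratory criterion. A count that causes no symptoms limits no activity, so only the mild grade fits, at any depth.

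**The case against.** The strongest reply is that the plan already counts neutropenia. Laboratory findings can be adverse events, clinically significant values are followed as such (sections 9.3 and 10.3), and incidence by preferred term (section 11.3.1) includes a recorded case whatever its grade. There are also tables of serious events and discontinuations, and section 11.4 supplies laboratory tables and event listings by group. Section 10.1.2 keeps severity apart from seriousness, so a mild grade does not prevent a serious classification. All of this stands. A reader might infer that neutropenia is examined only through means, or that it will be reported wrongly; the documents support neither.

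The route still has gaps. Section 6.6.1 sets explicit limits for platelets and GFR, but none is stated for neutrophils. Section 10.1 asks sites to record the diagnosis instead of its component signs, so a low count found during an infection may be absorbed into the infection. Section 10.2.3 names acute kidney injury and infections as the events of interest for risk-based monitoring.

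A reader might also infer that prednisone hides neutropenia. It does not: it would widen the mean gap and leaves the number of affected anakinra participants unchanged. Section 6.6.1 also speaks of leukocytosis, not neutrophils in particular.

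Two further objections have weight. Section 11.3 treats safety descriptively, and section 6.6.1, on liver injury, warns against looking for significance in rare events, so power is a poor yardstick and a new test is not called for. Section 11.1 refers to a Revised SAP for complete details. If that document already holds these tables, the tabulation gap closes.

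**Conclusion.** The point holds as a gap in specification. The stated laboratory analysis does not report the frequency or depth of low neutrophil counts, and its contrast between arms mixes any anakinra effect with a prednisone effect. The adverse event tables partly cover frequency, subject to what investigators record, and do not cover depth for symptomless cases. Under-counting is a possibility, not a demonstrated error, and no reported figure is shown to be wrong.

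The power figures are illustrations. They rest on assumed neutrophil distributions, an assumed value in affected participants, an assumed comparator rate and a cross-sectional SE that is not the planned mixed model. Within those limits, a threshold count does clearly better than means at 5–10% incidence against a near-zero comparator rate, and neither has useful power at 2%. The firmer argument is descriptive: at any incidence a count and percentage shows the cases, and a mean does not.

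The central and local laboratory statements contradict each other. That is a separate wording fault, but it must be settled before limits or reference ranges can be applied. Overall, the change is worth making because it is cheap and concerns a declared safety focus.

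**What to change.** 1. In sections 11.3.2 and 11.3.3 add, for absolute neutrophil count and platelets, the number and percent of participants in each arm whose worst post-baseline value falls below pre-stated graded reporting limits. State the time window.
2. Add baseline-to-worst shift tables, and a risk difference with confidence interval presented descriptively. No significance test is needed.
3. For laboratory-based adverse events, tabulate a grade derived from the laboratory value alongside Table 2 severity.
4. Reconcile sections 9.3 and 11.3.2 on central versus local laboratories. If testing is local, say how the eight sites' reference ranges are handled.
5. Include the table in the existing DSMB reports and the interim laboratory tables of section 11.4.

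The limits are for reporting only; nothing here sets a dose, hold or stopping rule. The cost is SAP wording, a few more programmed tables and two grading scales to explain. The blood counts are already drawn, so no new samples or visits are required.

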11.3.4 Other Safety Related Clinical Outcomes

The following clinical outcomes will be assessed:

- Death (from hepatic and non-hepatic related causes)
- Complications of portal hypertension including gastroesophageal bleeding, interventions to manage variceal bleeding (e.g., variceal banding/sclerotherapy or TIPS placement) and diuretic resistant ascites
- Complications of Cirrhosis: new-onset ascites, hepatic encephalopathy, hepatorenal syndrome (type I or II), and spontaneous bacterial peritonitis).
- Hospitalization
- Liver transplantation

11.4 Interim Analyses

Interim analyses for efficacy or futility to determine if the study may be terminated prior to completion will be conducted once after the cohort associated with at least 50% of the participants have been in the study for 90 days. Formal efficacy analyses will be based on the Lan-Demets version of the O'Brien-Fleming boundary to provide an overall two-sided $P = 0.05$ test. Futility will be assessed based on conditional power.^{57,58} For example, termination due to futility may be considered if conditional power is very low (e.g. less than 0.10), under the assumption that the hypothesized treatment difference is correct. In other words, based on data that become available at the interim analysis, assuming that the current trend continues, we should early stop the trial if the probability of declaring anakinra + zinc superior in the final analysis is low (e.g., less than 10%). We use this early stopping rule to limit patient exposure to a potentially ineffectual treatment.

The efficacy interim analyses will be performed on unblinded data. Additional data that will be included in the interim analyses are:

- Tables of laboratory data by group
- Tabulated safety data by group
- Listings of adverse events and serious adverse events by group

11.5 Handling of Missing Data

Missing values will not be imputed and only observed values will be used in data analyses and presentations.

11.6 Data and Safety Monitoring Board (DSMB)

An independent DSMB will be formed to review safety data at periodic intervals from this and all other AlcHepNet studies. Members of the DSMB will not be allowed to participate as investigators in this trial.

The DSMB will review blinded safety data and unblinded safety data (as necessary in their opinion) to ensure the safe and proper treatment of participants. The frequency of their standard meetings will be according to the agreed upon DSMB charter. In addition, Chair of the DSMB or the designated study physician may call for an ad-hoc DSMB if deemed necessary by either party. Based on review of these data, the DSMB will send a written report to the designated study physician and to the DCC-IU. It is the responsibility of the designated study physician and the DCC-IU to distribute

these reports to all other stakeholders (NIAAA, FDA, and individual sites)

The DSMB will operate under an appropriate charter (in compliance with relevant regulatory guidance) that will define its organization and operation. The DSMB will prepare written minutes of both its open and closed sessions. The closed minutes will be made available to the investigators only after the database is locked and the blind for the trial has been broken. All investigators and responsible IRBs will be informed of any decisions made which alter the conduct of this trial based on recommendations from the DSMB relating to participant safety. The investigators will inform the participants of such actions and the protocol and ICF will be revised, as appropriate.

Changes to the protocol or to the ICS may be initiated by any investigator, but it is the final responsibility of the designated study physician as the IND holder to approve/finalize any such changes and to communicate to other stakeholder.

